**Actual Primary Completion Date:** 

Actual Study Completion Date:

**Arms and Interventions:** 

Arm	Intervention/treatment	
Experimental: T Test	Drug: Valsartan and Amlodipine Tablets	
Test drug(Valsartan / Amlodipine)1 tablet	1 tablet contains Valsartan 80mg&	
contains Valsartan 80mg& Amlodipine	Amlodipine 5mg	
5mg		
Active Comparator: R Reference	Drug: Valsartan and Amlodipine Tablets	
Reference drug(Valsartan / Amlodipine)1	(I)	
tablet contains Valsartan 80mg&	1 tablet contains Valsartan 80mg&	
Amlodipine 5mg	Amlodipine 5mg	

### **Outcome Measures:**

Primary Outcome Measures:

Bioequivalence based on  $C_{max}$  [ Time Frame: Up to 96 hours post dose in each treatment period]

Bioequivalence based on AUC parameters [ Time Frame: Up to 96 hours post dose in each treatment period]

Secondary Outcome Measures:

Number of subjects with adverse events (AE)s [ Time Frame: Up to 96 hours post dose in each treatment period]

Safety and tolerability parameters will include recording of AEs

Safety assessed by vital sign measurement [ Time Frame: Up to 96 hours post dose in each treatment period]

Vital sign measurement will include blood pressure, pulse rate, respiration rate and ear temperature

Measure of clinical laboratory test values to access safety [ Time Frame: Up to 96 hours post dose in each treatment period]

Clinical laboratory tests will include blood biochemistry, CBC, urine routine examination and ECG.

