# **Study Details**

### **Study Description:**

**Brief Summary:** 

Comparative randomized, single dose, three periods, three-way crossover open-label study to determine the bioequivalence of Valsartan and Amlodipine Tablets (Hua yuan Pharmaceutical LLC, China) and Valsartan and Amlodipine Tablets (I) (Novartis Pharma Schweiz AG, Switzerland).

Condition or disease	Intervention/treatment	Phase
healthy	Drug: Valsartan and Amlodipine Tablets	The bioequivalence
	Drug: Valsartan and Amlodipine Tablets	study

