### **Study Design:**

Study Type: Interventional (Clinical Trial)

Actual Enrollment: 84 participants

Allocation: Randomized

Intervention Model: Crossover Assignment

Masking: None (Open Label)

Official Title: Comparative Open-label, Randomized, Fasting/Fed, Single Dose, Three-way

Crossover Bioequivalence Study of Valsartan and Amlodipine Tablets (Hua yuan

Pharmaceutical LLC, China) and Valsartan and Amlodipine Tablets ( I ) (Novartis Pharma

Schweiz AG, Switzerland)

Study Start Date:

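### The adverse-event outcome counts only the first 96 h after each dose, so it is a windowed count and not a study-wide one

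*Protocol*

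**What the plan says.** The Protocol's Outcome Measures section lists, as a secondary outcome, "Number of subjects with adverse events (AE)s [ Time Frame: Up to 96 hours post dose in each treatment period". The primary outcomes have the same time frame; for AUC the entry reads "Bioequivalence based on AUC parameters [ Time Frame: Up to 96 hours post dose in each treatment period". Vital signs have it too ("Safety assessed by vital sign measurement [ Time Frame: Up to 96 hours post dose in each treatment period"), and so do the laboratory tests.

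The only other sentence on collecting adverse events is "Safety and tolerability parameters will include recording of AEs", which gives no period. The Brief Summary describes the design as "Comparative randomized, single dose, three periods, three-way crossover open-label study", so there are two washouts and a time after the third dose. The Protocol does not say how long these are, and it sets no separate counting period for events that start in them.

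**The concern.** A 96 h limit is natural for concentration sampling. An adverse-event count answers a different question: how many subjects had an event while in the study. When the count takes the sampling window, it leaves out events starting later than 96 h after the first or second dose and before the next one, and events starting more than 96 h after the third dose.

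Because the outcome counts subjects and not events, a late event matters only when it is the subject's only one; that subject then adds nothing to the total. The total can equal the study-wide number but cannot exceed it. A reader who sees a number of subjects with adverse events, without the window beside it, may take it for the study-wide figure. What is at stake is how complete and how clearly labelled a secondary safety result is.

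**Working it through.** The Protocol states no adverse-event figure to reproduce, so the check is mainly a comparison of its wording.

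**Windows compared (Outcome Measures)**

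- Cmax: 0 to 96 h after each dose.
- AUC: the same.
- Number of subjects with adverse events: the same.
- Vital signs and laboratory tests: the same.
- Sentence on recording adverse events: no window.
- Other sections: no counting period for washouts or for follow-up after the third period.

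**Time covered.** Three single doses give 3 × 96 h = 288 h, or 12 days, per subject who completes all periods. The share of time in study that this represents cannot be worked out, because washout length and end of study are not given.

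**Illustration on assumed values only.** From the Protocol: 84 subjects (Study Design, "Actual Enrollment: 84 participants") and three periods. Assumed: all 84 complete three periods; the risk of an event per dose is p = 0.10; a share f of events starts after 96 h.

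*Independent periods, at most one event each.*

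- Study-wide count = 84 × (1 − (1 − p)³) = 84 × (1 − 0.9³) = 22.76.
- 96 h count = 84 × (1 − (1 − p(1 − f))³).
- f = 0: 22.76, missed 0.
- f = 0.05: 84 × (1 − 0.905³) = 21.74, missed 1.03.
- f = 0.10: 84 × (1 − 0.91³) = 20.70, missed 2.06.
- f = 0.20: 84 × (1 − 0.92³) = 18.59, missed 4.17.

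*The same subjects affected in every period.*

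- Study-wide count = 84 × 0.10 = 8.40.
- A subject is missed only if all three events are late: 84 × p × f³. At f = 0.20 this is 84 × 0.10 × 0.008 = 0.07.

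At p = 0.10 and f up to 0.20, the loss therefore runs from 0 to about 4 of 23 subjects, and almost disappears if events cluster in the same people. Neither p nor f comes from the Protocol, so this shows how the rule behaves and is not an estimate for this trial.

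**The case against.** The strongest reply is that nothing here is wrong. The window is clear and reproducible, and it is the same after every dose. A fixed post-dose window is a legitimate way to define a safety outcome, since it keeps the counted events close to the dose. The Protocol gives no event profile or timing that would show 96 h to be too short after a single dose. The text also reads like a registry summary: every outcome carries the same time-frame wording, and exclusion criterion 15 points to an appendix. A fuller document may set the collection period, and rules for assigning events to treatment are usually left to a statistical analysis plan.

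Much of this stands. There is no contradiction, inadequacy of the window is not demonstrated, and the choice is a trade-off. But the point does not rest on an omission. The Protocol states the window for this outcome, and a later analysis plan that counted washout events in it would depart from that stated time frame.

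Three stronger readings may suggest themselves, and the Protocol supports none of them:

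- *That later events are not recorded or are lost.* The sentence on recording sets no time limit, so later events may be on file. Only the defined count excludes them.
- *That the comparison of products is biased.* The same rule applies after test and reference, so the definition builds in no difference.
- *That a known number of subjects is missed.* That number depends wholly on assumed inputs, and zero is possible.

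**Conclusion.** The point holds as a minor improvement to safety reporting and not as a demonstrated error. As defined, the outcome is the number of subjects with an event in the first 96 h after a dose. It is at most equal to the number with an event at any time in the study.

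The size of the gap cannot be derived from the Protocol, and it is nil if no subject's only event starts outside the windows. The conclusion itself needs no numerical assumption; it follows from the stated time frame and the three-period design. It does assume that no fuller trial document sets a wider window for this outcome. The bioequivalence decision rests on Cmax and AUC and is untouched.

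**What to change.** Restate the time frame of the adverse-event outcome as first dose, through both washouts, to the end of the study. Assign each event to the last treatment taken before it started. Report the number of subjects with an event within 96 h of a dose beside the wider count, so that the present definition stays visible and the two can be compared. The PK time frames need no change.

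Cost: if later events are already recorded, one line of the outcome definition and one extra row in the safety table. If they are not, and the study is still running, adverse-event questions at the next period's admission and at the end of the study. The Protocol uses completed-study labels ("Actual Enrollment: 84 participants", "Actual Study Completion Date"), so the study may be over. In that case the wider count can use only events already on record; if there is no such record, label the reported figure as a 96 h count.

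Downside: a wider window will list some washout events that have nothing to do with either product. Showing both counts lets the reader see how many were added.

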## **Detailed Description:**

Primary Pharmacokinetic Parameters:  $C_{max}$ , Area under cover (AUC $_{0\rightarrow t}$  and AUC $_{0\rightarrow \infty}$ ). Secondary Pharmacokinetic Parameters:  $t_{max}$  and  $t_{1/2}$ . The method of judging bioequivalence of three-cross-section repeating experiment design: first of all, the calculation of the  $S_{WR}$  of the AUC and  $C_{max}$ , if  $S_{WR} \geqslant 0.294$ , the use of RSABE analysis; if Swr<0.294, the average Bioequivalence analysis method with Non-scale (bioequivalence limit is  $80\%\sim125\%$ ).

A comprehensive final report will be issued upon the completion of the study.

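### Does counting subjects with adverse events make the test product look safer because the reference is given twice?

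*Protocol*

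**What the plan says.** Under Outcome Measures, the first secondary outcome is "Number of subjects with adverse events (AE)s", with the time frame "Up to 96 hours post dose in each treatment period". The line beneath it says only that safety and tolerability will include the recording of events. It mentions no contrast between products, no test and no denominator.

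The Brief Summary describes a "single dose, three periods, three-way crossover open-label study". Arms and Interventions lists two products, the test product T and "Active Comparator: R Reference", each given as one tablet.

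The Detailed Description calls the trial a "three-cross-section repeating experiment design". S_WR is calculated first for AUC and Cmax. If it is at least 0.294, reference-scaled analysis is used; otherwise the rule is "the average Bioequivalence analysis method with Non-scale" with limits of 80% to 125%. The treatment sequences are not listed. Study Design gives an enrolment of 84, and the official title covers fasting and fed conditions without stating the split.

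**The concern.** S_WR can be estimated only from subjects who take R more than once. With two products and three periods, a subject who takes R twice has one period left for T. A count of subjects with at least one event then gives R two chances and T one, so R can look worse when the products are equal. If a single overall count is reported instead, it cannot show which product the events belong to.

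Either way, a test product with more events per dose might pass for one as safe as the reference. Adverse events head a short list of safety outcomes in the protocol, so the question deserves a check.

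**Working it through.** The protocol gives no event rate, so there is no figure of its own to reproduce. The check has two parts: how large the effect would be, and whether the protocol creates the conditions for it.

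**Inputs.** From the protocol: three single-dose periods, two products, 84 subjects. Assumed: event risk per dose p, the same for T and R; within-subject correlation ρ between events in two periods; all 84 subjects treated as one group. The ratios below do not depend on the fasting/fed split.

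**1. Partial replicate (TRR/RTR/RRT), both R periods merged per subject.**

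P(any event on T) = p

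P(any event on R) = 2p − [p² + ρp(1 − p)]

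| p | ρ | T | R | Subjects on T (×84) | Subjects on R (×84) | Ratio R/T |
|---|---|---|---|---|---|---|
| 0.05 | 0 | 0.05 | 0.0975 | 4.2 | 8.2 | 1.95 |
| 0.10 | 0 | 0.10 | 0.190 | 8.4 | 16.0 | 1.90 |
| 0.20 | 0 | 0.20 | 0.360 | 16.8 | 30.2 | 1.80 |
| 0.10 | 0.3 | 0.10 | 0.163 | 8.4 | 13.7 | 1.63 |
| 0.10 | 0.6 | 0.10 | 0.136 | 8.4 | 11.4 | 1.36 |
| 0.10 | 1 | 0.10 | 0.100 | 8.4 | 8.4 | 1.00 |

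Under these conditions the effect is real and can approach a factor of two.

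**2. Balanced three-period design (TRT/RTR), still merged per subject.** S_WR can be estimated here too, from the half of the subjects on RTR. For each product, 42 subjects have two doses and 42 have one. At p = 0.10 and ρ = 0:

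42 × 0.19 + 42 × 0.10 = 7.98 + 4.20 = 12.18 subjects for T, and the same for R.

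There is no bias in either direction. The need for S_WR alone therefore does not imply a count that favours T; the sequences would also have to be a partial replicate.

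**3. Counting by period, as the time frame indicates.** In any one period a subject takes one dose of one product. The number of subjects with an event in that period is therefore the number of administrations in that period with an event. In a partial replicate with equal allocation (assumed), each sequence has 84/3 = 28 subjects, so every period has 28 subjects on T and 56 on R. At p = 0.10, the expected counts per period are 2.8 of 28 on T and 5.6 of 56 on R. Over three periods this gives 8.4 of 84 T doses and 16.8 of 168 R doses, 10% for each. Correlation within a subject does not alter these expectations.

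**4. One overall count.** At p = 0.10 for both products and ρ = 0, 84 × (1 − 0.9³) = 84 × 0.271 = 22.8 subjects. The same total arises with T at 0.20 and R at 0.045, since 1 − 0.8 × 0.955² ≈ 0.271. An overall count indeed cannot separate the products. It does show how many volunteers had an event, and the protocol asks no more of it than that.

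**5. Does the protocol create the condition in step 1?** That bias needs three things: every subject on one T and two R, both R periods collapsed into one indicator, and the result set against T. The first is possible but not stated. The second and third appear nowhere in the protocol. The products are compared only on Cmax and AUC.

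**The case for a change.** The best case for the concern is that the protocol itself fixes the unit as the subject, so this challenges what is written and not only what is absent. The Brief Summary says three-way crossover in addition to three periods, which fits three sequences, and hence a partial replicate, better than two. The time frame names no product, and every period contains both T and R doses, so a count by period alone does not separate them. Readers will also compare any counts shown by arm, whether or not a formal comparison is planned.

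Part of this stands. The partial replicate is the likelier reading, a merged count would mislead under it, and attribution to product is not spelled out.

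The rest does not carry the point. Naming the subject as the unit does not exclude a count by administration, because the two coincide within a period (step 3). The randomisation fixes which product each subject takes in each period, so attribution needs no further data. The by-product layout of event tables and their denominators are ordinary content of a statistical analysis plan, and that document is not shown. A reader can be misled only by a table that merges the R periods, and the protocol does not ask for one.

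**Conclusion.** The concern does not hold. The outcome is a short label with a per-period time frame, and in a single-dose crossover that is enough to tie each event period to one product. The imbalance of up to about 1.7 to 2.0 times (for p from 0.30 down to 0.02, independent events) arises only under a partial replicate with the two reference periods merged and then compared with T. The protocol states no such merging and plans no such comparison. Under a balanced design the expected counts are equal, so a bias that always favours the test product cannot be claimed.

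This conclusion rests on reading the time frame as applying to each period separately, which is its plain sense. The event rates and correlations in the check are assumptions, but they affect only the size of the hypothetical bias. What remains is reporting detail for a descriptive safety outcome, with no bearing on the bioequivalence decision.

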## **Eligibility Criteria:**

Ages Eligible for Study: 18 Years to 45
Years (Adult)

Sexes Eligible for Study: All Accepts Healthy Volunteers: Yes

## Criteria

### Inclusion Criteria:

1. Healthy male or non-pregnant non-lactating female, age 18 to 45 years, including the critical value.

- 2. Male weight  $\geq$  50kg, female weight  $\geq$  45kg, body mass index (BMI) between 19 and 28kg / m2, including the critical value.
- 3. Good health, no heart, liver, kidney, digestive tract, nervous system, mental disorders and metabolic disease history.
- 4 Sign informed consent prior to the test and fully understand the contents, process and possible adverse reactions, and be able to communicate well with the researcher.

### **Exclusion Criteria:**

- 1. Any clinical trials in the 90 days prior to the trial, or other clinical trials planned for the duration of the trial.
- 2. Underwent major surgery within 90 days of the trial or planned to undergo surgery within 3 months of the trial.
- 3. Blood loss or blood donation over 300mL in the 90 days before the test.
- 4. Esophageal reflux, stomach bleeding or peptic ulcer disease in the 180 days prior to the test, heartburn occurs more than once a week, or any surgical procedure that may affect drug absorption (E.G. cholecystectomy).
- 5. Persons with specific allergies (asthma, urticaria, eczema, etc.) or allergies (such as those who are allergic to two or more medications, food or pollen), or are known to be allergic to the ingredients \* or analogues of the drug.
- \* The main components of the trial preparation: valsartan, benzene sulfonic acid amlodipine, microcrystalline cellulose, crosslinked povidone, crosslinked carboxymethyl cellulose sodium, silica, magnesium stearate, hydroxypropyl methyl cellulose, iron oxide yellow, polyethylene glycol, talc, Titanium dioxide; Reference Preparation main components: valsartan, amlodipine, microcrystalline cellulose, cross-linked povidone, silica, Magnesium stearate, hydroxypropyl methyl cellulose, iron oxide yellow, polyethylene glycol, talcum powder, Titanium Dioxide.
- 6. Use of any medication within 28 days of the trial, including prescription, over-the-counter, and/or alternative medications (such as medicinal herbs, herbal medicines, hemostasis and blood-activating plants or health supplements), and the use of hormonal contraceptives or vaccines.
- 7. A history of psychotropic substance abuse.
- 8. Urine screening Positive.
- 9. The average daily smoking was over 3 in the 90 days prior to the trial, alcohol consumption, women drinking more than 7 cups per week for 28 days or more than 14 cups per week for men (1 cups of =150ml wine =360ml Beer =45ml spirits).
- 10. Alcohol expiratory test Positive.
- 11. Body temperature (ear Temperature) ≥37.5°C, breathing is obviously abnormal and the researchers believe that it is not suitable to participate in the test, sitting systolic pressure >140mmhg or <100mmhg, sitting diastolic pressure >90mmhg or <60mmhg, sitting pulse 50 times/minute or > 100 Times/minute.
- 12. Human immunodeficiency virus antibody (HIV-Ab), hepatitis B virus surface antigen (HBsAg), hepatitis C virus antibody (HCV-Ab) or Treponema pallidum antibody (TP) Positive.
- 13. Special dietary requirements, No uniform diet during the trial.
- 14. Subjects refused to comply with the drug before 48h banned caffeine, alcohol, grapefruit

beverages and food (including tea, chocolate, coffee, coke, etc.).

- 15. Participants with a companion refused to use effective contraceptive measures within 180 days of screening to the completion of the test, as detailed in Appendix 2.
- 16. Female subjects were tested positive for blood/urine pregnancy.
- 17. Persons with impaired renal function, or who have suffered from urinary system disease.
- 18. A History of orthostatic hypotension.
- 19. fainting during venipuncture, dizzy blood and venous blood collection difficult person.
- 20. The physical examination was obviously abnormal and the researchers found it inappropriate to participate in the trial.
- 21. There was a significant abnormality in the ECG test and the researchers found it inappropriate to Participate.
- 22. Blood biochemistry, blood routine, urine routine examination had the obvious abnormality and the researcher thought that was not suitable to participate in the experiment.
- 23. Subjects may not be able to complete this study or other researchers ' judgment for other reasons.

Note: the exclusion criteria in 1th, 2, 3, 4, 6, 9 in the time are from the first 1 days before the administration of the Calculation.

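### Does the missing comparison sign before the lower pulse figure in exclusion criterion 11 leave screening without a lower pulse limit?

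*Protocol*

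**What the plan says.** Item 11 of the protocol's Exclusion Criteria sets limits for ear temperature, blood pressure and pulse, and leaves abnormal breathing to the researchers' judgement. Systolic pressure has a two-sided rule, "sitting systolic pressure >140mmhg or <100mmhg". Diastolic pressure has the same form, and pulse follows directly: "sitting diastolic pressure >90mmhg or <60mmhg, sitting pulse 50 times/minute or > 100 Times/minute".

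Pulse appears once more, under Outcome Measures, as one of the vital signs recorded for safety. No limit is given there.

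Elsewhere the protocol does say how boundary values are treated. Inclusion criterion 2, for example, has "body mass index (BMI) between 19 and 28kg / m2, including the critical value", and inclusion criterion 1 does the same for age.

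Three further exclusion criteria rest on judgement and could catch a volunteer with a worrying slow pulse: item 20 ("The physical examination was obviously abnormal and the researchers found it inappropriate to participate in the trial"), item 21 ("There was a significant abnormality in the ECG test and the researchers found it inappropriate to Participate") and item 23 ("Subjects may not be able to complete this study or other researchers ' judgment for other reasons").

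Study Design gives "Actual Enrollment: 84 participants".

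**The concern.** Eligibility limits belong in the protocol, and this one is an operative rule for screening healthy volunteers. Criterion 11 itself separates matters left to judgement (breathing) from matters fixed by a number (temperature, pressure, pulse), so an objective pulse rule was evidently intended. If the lower half of that rule has no direction, different screeners could treat a slow pulse differently, and an auditor could not say who had been enrolled in breach of the criterion.

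The boundary looks exposed as well. The protocol states that the end values count for age and BMI, but for the lower pulse figure it states neither the direction nor whether 50 itself excludes. At stake would be uniform screening at the slow end of the pulse range.

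**Working it through.** No arithmetic beyond counting applies, and the plan has no computed figure to reproduce on this point. The check sets the limits in criterion 11 side by side and asks how far the possible readings differ.

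**Step 1. The limits in criterion 11.**

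| Measure | Upper exclusion limit | Lower exclusion limit |
|---|---|---|
| Ear temperature (°C) | ≥37.5 | none given |
| Systolic pressure (mmHg) | >140 | <100 |
| Diastolic pressure (mmHg) | >90 | <60 |
| Pulse (per minute) | >100 | 50, no sign |

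Numeric limits: 1 + 2 + 2 + 2 = 7. With a sign: 6. Without: 1.

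**Step 2. Is the limit stated elsewhere?** No. The only other mention of pulse, under Outcome Measures, has no number.

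**Step 3. The possible readings of** "sitting pulse 50 times/minute or > 100 Times/minute".

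| Reading | Pulse 49 | Pulse 50 | Pulse 51 to 100 | Pulse above 100 |
|---|---|---|---|---|
| (a) Word for word: exactly 50, or above 100 | eligible | excluded | eligible | excluded |
| (b) Below 50, or above 100 | excluded | eligible | eligible | excluded |
| (c) 50 or below, or above 100 | excluded | excluded | eligible | excluded |

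**Step 4. Which readings survive?** Reading (a) would turn away a volunteer at 50 and admit one at 49 or lower. No screener would apply that. Both blood-pressure limits in the same sentence are pairs of exclusion values with a middle range left eligible, and the pulse limit has the same paired form. The 50 is therefore the lower cut-off, which leaves (b) and (c).

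**Step 5. How far apart are (b) and (c)?** They agree at every pulse from 49 down and from 51 up. They differ at one whole-number value, exactly 50 per minute. The sentence leans one way without settling it: the other five pressure and pulse signs are strict, and the only inclusive sign is on the one-sided temperature limit.

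**Step 6. Does anything downstream depend on it?** The Detailed Description bases the bioequivalence decision on the within-subject standard deviation of the reference product for AUC and Cmax: the scaled method at 0.294 or above, otherwise the 80% to 125% limits. Pulse does not enter. In a three-period crossover each participant is compared with himself or herself, so admitting or refusing someone at exactly 50 would not favour test or reference.

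**The case for a change.** The strongest case for acting is that the defect is verifiable, sits in a rule meant to be objective, and costs one character to mend. Judgement under items 20, 21 and 23 is not a substitute for a fixed limit, and pulse is one of the trial's own safety measurements. Loss in PDF reading is an uncertain excuse, since the comparison signs on the neighbouring limits survived, including two less-than signs in the same sentence. The status of exactly 50 cannot be derived from the text, because the sentence uses both strict and inclusive signs.

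Most of this stands as description. The sign is absent from the text at hand, no other section supplies it, and the boundary value is unstated. A lost character is unlikely, but the extracted text alone cannot exclude it.

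What does not stand is the step from there to a rule without a lower limit. That needs the word-for-word reading, which admits 49 and refuses 50 and so cannot be what anyone applied. On the readings that remain, uniform application is in doubt for one pulse value only, and the documents do not show that any participant had it. The age and BMI wording adds little: those criteria are written as ranges, whose end points need a statement, whereas criterion 11 works with signs.

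The benefit of acting is also small. Enrolment is listed as actual, so corrected wording would no longer steer screening in this trial, and a look at the screening records would concern conduct rather than the plan.

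**Conclusion.** The observation is correct but clerical. One of seven limits in criterion 11 lacks its comparison sign. The context fixes 50 as the lower pulse cut-off, and the only open question is a pulse of exactly 50 per minute. Analysis and conclusions on Cmax and AUC are unaffected, and no change to the plan is needed.

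This rests on two assumptions. Screeners applied the evident two-sided rule, as the paired blood-pressure limits lead any reader to do. Pulse was recorded in whole numbers, so that the two plausible readings part at a single value. How many of the 84 participants, if any, had that value at screening cannot be seen from the protocol. Whether 50 itself excludes is for the sponsor to say, and nothing here favours one clinical limit over another.
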